#### **8.1.3 Adverse Drug Reaction (ADR)**

Adverse Drug Reaction (ADR): any untoward and unintended responses to an investigational medicinal product related to any dose administered (having a reasonable causal relationship to the product, the term “reasonable causal relationship” meaning that there is evidence or arguments to suggest a causal relationship).

Unexpected ADR: an adverse reaction whose nature, severity, specificity, or outcome is not consistent with the applicable product information (e.g., Investigator’s Brochure)

#### **8.1.4 Serious Adverse Reaction (SAR)**

Serious Adverse Reaction (SAR): any untoward and unintended responses to an investigational medicinal product related to any dose administered (having a reasonable causal relationship to the product, the term “reasonable causal relationship” meaning that there is evidence or arguments to suggest a causal relationship), and that results in death, is life-threatening, requires patient hospitalization or prolongation of existing hospitalization, results in persistent or significant disability or incapacity, or is a congenital anomaly or birth defect or is medically important.

#### **8.1.5 Serious Adverse Safety/Quality Event (SASQE)**

An Adverse Safety/Quality Event (SASQE) is any adverse event related to any operation done on the collected human biological material under the responsibility of the Intermediary Structure (i.e., direct transport and distribution of the human biological material from the harvesting site to the Production/Tissue Establishment of Bone Therapeutics S.A.) that may cause death, be life-threatening, generate disability or incapacity to work to the patient, or that may cause morbidity.

### **8.2 Reporting of Adverse Events**

The occurrence of AE/SAE (drug- or procedure- or study-related) will be assessed by non-directive questioning of the subject since the beginning of the study at the screening visit, and each follow-up visit searching for any changes in health status (e.g., "Have any Adverse events

or Serious adverse events occurred since the last visit?"). Furthermore, AE/SAE volunteered by the patient during or between the follow-up visits, or detected through observation, physical examination (including body mass index and vital signs), laboratory testing, or other clinical procedures during the observation period will be documented. Patients will be instructed that they must immediately report any adverse events, subjective complaints, or objective changes in their well-being to the Investigator or site personnel, regardless of the perceived relationship between the event and the test product.

If it is determined that an AE/SAE has occurred, the Investigator should obtain all the information required to complete the corresponding AE or SAE Form of the CRF, and establish potential causality relationship with the product or the surgical procedure.

#### 8.2.1 Observation period for the occurrence of AEs and SAEs

**Table 9: Observation Period for the Occurrence of AEs and SAEs**

Start of Study AE/SAE Observation Period	At ICF signature
End of Study AE/SAE Observation Period	6 months after Implantation

[REDACTED]  
[REDACTED]  
[REDACTED]  
[REDACTED]

### 8.2.2 Summary of Possible Risks related to the Procedures

**Table 10: Summary of Possible Risks related to the Procedures**

	AE	SAE (Fatal and Non-Fatal)
ALLOB® Implantation	Surgery Pain at the implantation site Local haematoma Infectious complications  Anaesthesia Haematoma Irritation Infection Lipothymia Paraesthesia Transient hypotension Nausea and vomiting	Surgery Haemorrhage Sepsis Shock Infectious complications  Anaesthesia Allergy Infection Systemic toxicity Respiratory arrest Cardiac complications Myocardial infarction Cardiopulmonary arrest Ventricular tachycardia Neurological complications Stroke Pulmonary complications Inhalation pneumonia Pulmonary embolism Anaphylactic shock
Blood Sampling	Pain at the sampling site Local haematoma Superficial vein thrombosis Transient hypotension	Syncope

**ALLOB-DU1 - Clinical Study Protocol**

ALLOB-DU1\_CSP

V 05

Author: [name]

February 02, 2017

Pg. 82/136

**8.2.3 Summary of Adverse Drug Reactions and Possible Risks related to the Product and/or to the Procedures**

There is no reported ADR with ALLOB® at this stage.

However, PREOB®, an autologous osteoblastic cell product, has been administered in humans in phase I/IIa and IIb studies. A summary of observed adverse events possibly related to study treatment (i.e., PREOB® and/or the implantation procedure) is listed in Table 11.

**Table 11: Summary of Observed Adverse Events (AE) and Serious Adverse Events (SAE) possibly related to Study Treatment (i.e., PREOB® and/or the Implantation Procedure)**

Non-Serious AE		SAE (Non-Fatal)	
Total	27.0%	Total	3.2%
Pyrexia	7.9%	Systemic inflammatory response syndrome	1.6%
Pain	17.5%	Pancytopenia**	1.6%
Pain (general disorders)	6.3%	Pyrexia**	1.6%
Procedural Pain	4.8%	Altered status of consciousness**	1.6%
Musculoskeletal Pain	3.2%		1.6%
Arthralgia	1.6%		
Pain in extremity	1.6%	Hypotension**	
Urinary retention	1.6%		
Post-procedural haematoma	1.6%		
Post-procedural bleeding	1.6%		

\* AEs and SAEs were limited to TEAEs and STEAEs and reported per Preferred Term (PT) (MedDRA coding), along with their frequency of occurrence in subjects. Subjects were counted once for each PT. An AE/SAE was considered as treatment-emergent if it occurred on or after the date of the IMP implantation. In case of missing start date, the AE was considered as treatment-emergent. \*\* 4 SAEs were reported in the same patient.

**8.2.4 Assessment of the Safety Monitoring Committee**

A review of all the reported SAE potentially related to the IMP, and especially those related to immunological reactions (severe AESCs), will be done by the Safety Monitoring Committee

(SMC) after the inclusion of each block of 4 patients until the inclusion of the first 16 patients. This review will cover all SAE potentially related to the IMP from the day of treatment to the first 15 days of follow-up for the first block of 4 patients and from the day of treatment to the end of hospitalization period for the second, third and fourth blocks of 4 patients.

The main conclusions and decisions will be communicated to all Investigators 48 hours after each meeting. A report will subsequently be prepared and its summary submitted to the IECs and CAs. The SMC will be composed by a Safety Consultant and one medically qualified member of the Sponsor. This committee will decide whether the study can be continued as planned. If the decision is to stop or modify the study, it will be communicated by the Sponsor to the Investigators of all centres within 48 hours, the IECs and CAs.

After the review of the fourth block of 4 patients, the recruitment will continue (up to maximum 32 treated patients) and no more safety committee will be performed for all the subsequent treated patients. The safety of all patients will be monitored regularly as described in the study protocol and documented as appropriate.

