**Patient Inclusion Scheme:**

In order to maximise patient safety, for the first 16 patients treated, patient recruitment will proceed stepwise by blocks of 4. Full first 2 weeks safety data of the first block of 4 treated patients will be analysed before the first patient of the second block of 4 is treated. First 48 hours safety data of the second block of 4 treated patients will be analysed before treatment of the first patient of the next block. This latter scheme will be repeated until 16 patients have been treated. This review of reported SAE potentially related to the Investigational Medicinal Product (IMP), and especially those related to immunological reactions (severe Adverse Event of Special Consideration (AESc)), will be done by the Safety Monitoring Committee (SMC).

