**Study Endpoints and Criteria for Evaluation****Safety Criteria**

In addition to standard pharmacovigilance requirements, particular attention will be given to AE suggesting immune-mediated reactions, such as: general discomfort, uneasiness, ill feeling, pain or swelling in the implanted area, fever and any inflammatory reactions, flu-like symptoms (e.g., chills, body aches, shortness of breath, cutaneous rashes...). All severe AEs potentially related to the IMP and in particular those potentially related to the allogeneic reactions will be managed by the SMC who will analyse and report these events in a timely manner consistent with the safety of patient recruitment scheme.

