## ALLOB-DU1 - Clinical Study Protocol

ALLOB-DU1_CSP	V 05	Author: [name]	February 02, 2017	Pg. 22/136
---------------	------	-------------	-------------------	------------

- **Investigator:** a person responsible for the conduct of the clinical trial at a trial site. If a trial is conducted by a team of individuals at a trial site, the investigator is the responsible leader of the team and may be called the principal investigator.
- **Managing Physician (or delegate):** managing Physician of Human Biological Material in the Production/Tissue Establishment, is a Medical Doctor responsible to guaranty the traceability, the quality and safety of the Human Biological Material, as well as the quality and safety of all operations executed in the Production/Tissue Establishment. He is also responsible for the reporting of Serious Adverse Event and Serious Adverse Reaction related to Human Biological Material. His function can be delegated.
- **Mesenchymal Stromal Cells:** “plastic-adherent” stem cells, expressing specific surface markers, and giving rise to bone, cartilage, and adipocyte cells.
- **Non-union fracture:** refers to a fracture that will not unite within 6 to 9 months and needs additional surgical or non-surgical intervention
- **Osteoblastic cells:** cells belonging to the osteoblastic lineage (bone forming cells) encompassing the osteoprogenitors, the pre-osteoblasts, the osteoblasts, the lining cells and the osteocytes.
- **Osteoprogenitor cells or osteoprogenitors & pre-osteoblasts:** are not-fully differentiated cells committed to the osteoblastic lineage, i.e., precursors of osteoblast displaying limited proliferation capacity.
- **Processing:** all operations involved in the preparation, manipulation, preservation, and packaging of tissues or cells intended for human applications
- **Randomised patient:** patient to whom a randomisation number has been allocated
- **Screened patient:** a patient who has dated and signed the Informed Consent Form (ICF) (enrolled patient) and who has performed the checking of the selection criteria.
- **Screening failure:** a screened patient who is not eligible for the study after checking the selection criteria.
- **Safety Monitoring Committee (SMC):** a committee established by the Sponsor to analyse, for each block of 4 patients from the first 16 patients, the safety data and make recommendations whether to continue or stop the trial.

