### 2.2.1 Safety

From Visit #1 to the end of the main study period at Month 6, subjects will be systematically assessed for the potential occurrence of any AE or SAE, related to the product or related to the procedure, using patient open questionnaires, physical examination, (including vital signs), and laboratory measurements.

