## 2.5 Patient inclusion scheme

With the objective of maximum 32 patients treated in the study, and taking into account 10% drop-out, 35 patients will be enrolled.

For the first 16 patients, the patient recruitment will proceed stepwise by blocks of 4. Full first 2 weeks safety data of the first block of 4 patients will be analysed before the first patient of the second block of 4 patients is treated. First 48 hours safety data of the second block of 4 patients will be analysed before treating the first patient of the next block. This latter scheme will be repeated until the first 16 patients have been treated.

A Data Safety Monitoring Board (DSMB) will be established to assess the safety and efficacy when 6-month post treatment results for the first 16 assessable patients will be available (i.e., interim analysis). This Board will recommend to the Sponsor whether to continue, modify or stop the trial. The study can be prematurely stopped:

- For safety concerns
- For futility if less than 4 successes are observed
- For efficacy if 12 or more successes are observed

Additional patients can otherwise be treated in order to reach a total of 32 patients.

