### 10.9 Safety Follow-up

For the first 16 patients, patients will be treated in the study by sub-group (block) of 4. Before starting the treatment of a new block of 4 patients, a safety review at the end of the Visit #3 for the first block (48 hours of hospitalization and first follow-up visit at 2 weeks after implantation) and at the end of Visit #2 (48 hours hospitalisation or on-site visit) for the other blocks will be conducted. If from this review, 3 or more patients have not experienced SAE potentially related to the IMP, including severe AESC, and resulting in death, life-threatening, resulting in persistent or significant disability/incapacity, requiring intervention to prevent permanent impairment or damage, the next block of 4 patients will be allowed for treatment (Visit #2).

The members of the SMC will perform this safety monitoring analysis.

After inclusion of the first 16 assessable patients and based on 6-month treatment follow-up, a safety and efficacy interim analysis will be planned.

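### The block-release criterion in 10.9 leaves out serious events attributed only to the implantation procedure, and the protocol states the SMC's review scope in two conflicting ways

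*Combined protocol and SAP*

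**What the plan says.** **Release criterion.** Section 10.9 looks at each block of 4. If "3 or more patients have not experienced SAE potentially related to the IMP" with one of the listed outcomes (death, threat to life, lasting disability, or intervention needed to prevent permanent damage), then "the next block of 4 patients will be allowed for treatment". The SMC members carry out this review.

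**SMC scope, narrow wording.** Section 8.2.4 says "This review will cover all SAE potentially related to the IMP". The synopsis (Patient Inclusion Scheme) uses the same limit: "This review of reported SAE potentially related to the Investigational Medicinal Product (IMP), and especially those related to immunological reactions". The synopsis Safety Criteria extend the remit beyond SAEs, but still on the product side only: "All severe AEs potentially related to the IMP and in particular those potentially related to the allogeneic reactions will be managed by the SMC".

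**SMC scope, broad wording.** The Definitions of Terms set up the SMC "to analyse, for each block of 4 patients from the first 16 patients, the safety data", with no causality filter. Section 2.5 says "Full first 2 weeks safety data of the first block of 4 patients will be analysed", and the synopsis and 7.1 say much the same.

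**Procedure-related events elsewhere.** The safety objective in 2.2.1 covers "any AE or SAE, related to the product or related to the procedure". The SAE form in 8.3.1.2 records causality to the trial procedures separately from causality to the IMP. Table 10 (8.2.2) lists haemorrhage, sepsis, shock and infectious complications as possible SAEs of the implantation surgery.

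**The concern.** Every patient in this single-arm study receives the cells through a trephine under anaesthesia, so the next block faces the product risk and the procedure risk together. The protocol treats both as safety outcomes in its objective, its SAE form and its annual safety reports. The staged-inclusion criterion is the exception, and no reason is given. Read literally, all 4 patients in a block could have a life-threatening event attributed only to the implantation and the criterion would still be met.

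The two descriptions of the SMC's scope make this harder to settle in practice. A committee following 8.2.4 would look at IMP-related SAEs. One following its own definition would look at all the block's safety data. At stake is whether a cluster of serious surgical complications, or a mixture of product and procedural ones, triggers the formal hold or depends on the committee's discretion.

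**Working it through.** The plan gives no operating characteristic for the 3-of-4 rule, so there is no stated figure to reproduce. The check has two parts.

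**1. Which events count.**

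| Event in the block, with a listed outcome | Counts under 10.9 now | Counts if the procedure is added |
|---|---|---|
| Potentially related to the IMP | Yes | Yes |
| Related to both IMP and implantation | Yes | Yes |
| Attributed by investigator and sponsor to the implantation only | No | Yes |
| Related to neither | No | No |

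A case where the answer changes: one patient has a counted IMP-related SAE and another an equally severe SAE attributed only to the implantation. Now, 3 of 4 are free and the criterion is met. With the procedure included, 2 of 4 are free and it is not.

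**2. How often a block would fail.** Let q be the probability that a patient has a counted SAE in the review window, with patients independent. The block fails if 2 or more of 4 are affected:

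P(fail) = 1 − (1 − q)^4 − 4q(1 − q)^3

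- q = 1.6%: 1 − 0.9375 − 0.0610 = 0.0015
- q = 3.2%: 1 − 0.8780 − 0.1161 = 0.0059
- q = 5%: 1 − 0.8145 − 0.1715 = 0.0140

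These values of q are assumptions. The nearest figure in the documents is in Table 11 (8.2.3), where 3.2% of subjects had an SAE possibly related to PREOB and/or its implantation; 1.6% is half of that. It is only a loose guide. PREOB is a different, autologous product. The figure combines product and procedure, is not limited to the outcomes in 10.9, and has no stated 48-hour limit, whereas the reviews after the first block cover about 48 hours.

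The gain from widening the criterion is the difference between the failure probabilities under the two wordings. If the total counted rate were 3.2%:

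- none IMP-related: 0.59% − 0 = 0.59 percentage points per block
- half IMP-related: 0.59% − 0.15% = 0.44 percentage points
- all IMP-related: 0.59% − 0.59% = 0

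At an assumed total of 5% the gain is at most 1.4 percentage points per block.

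**The case against.** The best defence is that the staged blocks exist to detect allogeneic and immunological reactions, so a product-focused trigger is coherent. The gap is also narrow. Under 8.1.2 an event counts as IMP-related if either the investigator or the sponsor suspects it, the test is whether a causal link is reasonably possible, and the sponsor should not downgrade the investigator's view. Most events that are hard to assign would already count. The serious events in Table 11 are mainly systemic (inflammatory response, pancytopenia, hypotension), which an assessor of a cell product might well call potentially IMP-related. All of this stands and limits the size of the point. It does not alter what 10.9 counts.

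A reader might go further and infer that procedure-only SAEs need not reach the SMC at all, or that they escape oversight. The documents do not support that:

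- The SMC definition, and the safety-data wording in the synopsis, 2.5 and 7.1, carry no causality filter. The narrow wording in 8.2.4 conflicts with them but does not clearly override them.
- Under 8.3.1.2 every SAE is notified within 24 hours whatever its attribution, and SAEs related to trial procedures are individually notified to ethics committees, investigators and the sponsor.
- One SMC member comes from the sponsor, and 8.2.4 lets the committee stop or modify the study. Meeting the 3-of-4 criterion permits the next block but does not remove that power.

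**Conclusion.** The point holds in a limited form. The 10.9 criterion counts only SAEs potentially related to the IMP, so a severe SAE attributed solely to the implantation does not count toward holding the next block. The protocol also conflicts with itself on whether the SMC reviews IMP-related SAEs or all of the block's safety data. This is worth a wording correction; it is not a failure of safety oversight.

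The numerical effect is small: at the assumed rates above, the extra chance of a hold is between 0 and about 1.4 percentage points per block. That range depends on rates the documents do not give, on independence between patients, and on one rate serving both the 2-week and the 48-hour windows. The case for the change rests mainly on consistency with the protocol's own safety objective and on removing the ambiguity about scope.

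**What to change.** - **8.2.4 and synopsis (Patient Inclusion Scheme):** state that the SMC reviews a listing of all SAEs in the block whatever their attribution, in line with the SMC definition. The special attention to immunological reactions can stay.
- **10.9:** keep the listed outcomes and the 3-of-4 threshold, but count SAEs potentially related to the IMP, the implantation procedure or both. Define the procedure by the category already on the SAE form, which groups implantation, surgery and anaesthesia. Exclude only events attributed solely to blood sampling. Anaesthesia should stay in: the form and Table 10 both place it under the implantation, and every patient receives it with the cells.

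The cost is wording in three places and one listing from data already collected. The downside is a rare hold for a procedural complication and a few more events for the SMC to review. The documents give no basis for estimating how many, since the listing would also include SAEs unrelated to treatment.

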**Detailed visit schedule**

After informed consent is obtained, fulfilment of study inclusion and exclusion criteria will be performed at Visit #1, which will take up to 8 weeks to complete. Visit #2 is scheduled to take place after completion of Visit #1 for baseline clinical assessments and ALLOB® implantation (the baseline of the radiological assessments is Visit #1). At Visit #2, all patients will be hospitalized for 24 or 48 hours after implantation, according to the judgment of the Investigator.

Patients will be followed during 6 months, at 2 weeks, 1, 3, and 6 months (Visit #3 to Visit #6).

[REDACTED]

[REDACTED]

[REDACTED]

[REDACTED]

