**5.3 Peri-operative antibiotic therapy and other medication**

All patients will receive a single intravenous infusion of cefazolin (2g) or any standard-of-care antibiotic therapy used at the investigating site at induction. Besides, drugs used during anaesthesia will not be systematically recorded in the CRF, except if an Adverse Event should have occurred.

Patients will be hospitalized for 24 or 48 hours, upon Investigator's judgement ( [REDACTED] [REDACTED] ). If patients are hospitalized for 24 hours, they must return to the Investigating Site for the Visit #2 – 48h post-implantation visit.

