## 7. SAFETY AND TOLERABILITY MEASUREMENTS AND ENDPOINTS

## 7.1 Overview of Safety Parameters and Endpoints

The safety and tolerability of the test product (ALLOB®) will be systematically investigated throughout the study period. Patients will be evaluated at each follow-up visit for the potential occurrence of any AE or SAE, related to either the product or the study procedures. Definitions of AE/SAE are in Section 8.

For the first 16 patients, recruitment will proceed stepwise by blocks of 4. Full first 2 weeks safety data of the first block of 4 patients will be analysed before the first patient of the second block will be treated. First 48 hours safety data of the second block of 4 patients will be analysed before treating the first patient of the next block. This latter scheme will be repeated until the 16th patient has been treated.

Table 6 below shows how the safety endpoints of this study relate to the study objectives. Assessments and measurements will be carried out at the times specified in the study Flow Chart (see above).

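### Section 8.2.4 closes the Safety Monitoring Committee's window for blocks 2 to 4 at hospital discharge, possibly 24 hours, while Section 10.9 and three other places require 48 hours

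*Combined protocol and SAP*

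**What the plan says.** The first 16 patients are treated in blocks of 4, and the Safety Monitoring Committee reviews each block. Section 8.2.4, which describes that review, says that for the later blocks it covers serious adverse events potentially related to the product "from the day of treatment to the end of hospitalization period for the second, third and fourth blocks of 4 patients".

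Section 10.9 assigns the review to the same committee and sets it "at the end of Visit #2 (48 hours hospitalisation or on-site visit) for the other blocks". It also contains the release rule: the next block may be treated if 3 or more patients are free of the specified serious events.

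Three other places use 48 hours:

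- Synopsis, Patient Inclusion Scheme: "First 48 hours safety data of the second block of 4 treated patients will be analysed".
- Section 2.5: "First 48 hours safety data of the second block of 4 patients will be analysed before treating the first patient of the next block".
- Section 7.1 repeats the requirement.

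On length of stay, the synopsis says that "all patients will be hospitalized for 24 or 48 hours after implantation", at the investigator's judgement. Section 5.3 gives the same choice and adds: "If patients are hospitalized for 24 hours, they must return to the Investigating Site for the Visit #2", namely its 48-hour post-implantation part.

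After the fourth block, Section 8.2.4 states that "no more safety committee will be performed for all the subsequent treated patients".

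**The concern.** Discharge and the 48-hour assessment are separate events for any patient sent home at 24 hours. A window that ends at discharge stops short of the 48-hour visit, whereas one that ends with Visit #2 includes it. The protocol thus gives two different cut-offs for one review by one committee.

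The review decides whether the next block of patients receives an allogeneic cell product, and it looks especially for immunological reactions. Section 8.2.4 carries the committee's name in its heading, so its members may well turn to it for their remit. A committee working from that section alone could close a block without the 48-hour visit data. The 48-hour design itself is not in question; the point is that one section does not match it.

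**Working it through.** No sample size, power or error rate is involved, so there is no statistical figure to reproduce. The check compares the texts and counts the patients who could be affected.

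**The stated windows for blocks after the first**

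| Place | End of window |
|---|---|
| Synopsis, Patient Inclusion Scheme | 48 hours |
| Section 2.5 | 48 hours |
| Section 7.1 | 48 hours |
| Section 10.9 | End of Visit #2: 48 hours, in hospital or at the on-site visit |
| Section 8.2.4 | End of hospitalization |

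**Applying the length of stay (synopsis and Section 5.3)**

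- Patient kept 48 hours: the Section 8.2.4 window ends at 48 hours, and all five places agree.
- Patient discharged at 24 hours: the Section 8.2.4 window ends at about 24 hours, and the other four end at 48 hours. Interval left out: 48 − 24 = 24 hours, including the mandatory return visit.

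**Ceiling on patients affected**

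- Blocks 2 and 3, whose 48-hour review comes before release of another block of 4: 2 × 4 = 8 patients.
- Block 4, which releases no further block of 4 but is the committee's last review: 4 patients.

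The floor is 0, because the protocol does not say how many patients leave at 24 hours and the text beside that choice in Section 5.3 is redacted.

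**How the difference could matter to a decision (illustration only)**

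Under Section 10.9 a block passes if at least 3 of its 4 patients are free of the specified events, so 4 − 3 = 1 affected patient is tolerated. Suppose one patient has a qualifying event within 24 hours, and a second, discharged at 24 hours, has one at hour 30.

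- Counting to 48 hours: 2 affected, 4 − 2 = 2 free, fewer than 3. The criterion for release is not met.
- Counting only to discharge, as in Section 8.2.4: 1 affected, 4 − 1 = 3 free. The criterion is met.

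This shows that the two cut-offs can give opposite answers. It says nothing about how likely that is.

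**The case against.** The strongest reply is that the safeguard is already in place. The 48-hour requirement appears in four places. Section 10.9 names the committee, provides for early discharge, and is the only section with the 3-or-more rule, so anyone applying that rule reads the 48-hour timing in the same paragraph. The 48-hour visit is compulsory, and Section 8.3.1.2 requires serious adverse events to be notified within 24 hours of occurrence or awareness. Nothing in Section 8.2.4 allows the next block to start early. All of this stands, and it is why the practical effect is limited.

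A second reply is that Section 8.2.4 is loosely worded and uses the hospital stay as shorthand for Visit #2; for the first block it likewise says 15 days where other sections say 2 weeks. This is a plausible account of how the phrase arose, but it does not remove the conflict. Section 10.9 names the on-site visit as an alternative to 48 hours in hospital, and Section 8.2.4 does not.

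A third is that Section 10.9 says when the review takes place and Section 8.2.4 what it covers. A review held at 48 hours whose coverage stops at discharge still leaves out hours 24 to 48 for a patient sent home at 24.

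Finally, the redactions in Section 5.3 and in the Visit #2 procedures may hide conditions on 24-hour discharge. That limits what can be said about the number affected, not about the difference in wording.

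**Conclusion.** The concern holds. Section 8.2.4 is the outlier among five statements of the same safety window, and as written it is wrong for any patient discharged at 24 hours. The gap is 24 hours per such patient, for between 0 and 8 patients in blocks 2 and 3 and between 0 and 4 in block 4. These ceilings assume full blocks of 4 and discharge at 24 hours for everyone in them.

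This is a minor internal inconsistency. It changes no endpoint, analysis or visit, and the 48-hour gate survives elsewhere in the protocol. Confidence is high that the texts differ; whether any patient would be affected cannot be determined from the document.

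**What to change.** In Section 8.2.4, for the second, third and fourth blocks, replace the end of hospitalization as the cut-off with 48 hours post-implantation (in hospital or at the on-site 48-hour visit), to match Section 10.9.

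The cost is one phrase. No visit, procedure or data item is added, because the 48-hour visit is already mandatory for patients discharged at 24 hours.
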